Study Centers Approximately 15 sites in the US		
Phase of Development Phase 2a		
Study Objectives Primary Efficacy 
To assess the efficacy of both dose levels of miricorilant versus placebo in reducing liver fat content. Secondary Efficacy 
To assess the efficacy of both dose levels of miricorilant combined versus placebo in reducing liver fat content.To assess the efficacy of miricorilant versus placebo on change in biomarkers of NASH disease activity. Exploratory 
To be assessed by patient group:
In all patients, change in adrenocorticotrophic hormone (ACTH), serum cortisol, serum aldosterone, absolute body weight, and insulin resistance.In patients with diabetes, change in glycated hemoglobin A1c (HbA1c) and fasting blood glucose.In patients with high blood pressure, change in blood pressure.To evaluate the dose-response relationship between miricorilant and change in liver fat content.To evaluate the exposure-response relationship between miricorilant and change in liver fat content. Safety 
To assess the safety and tolerability of miricorilant versus placebo. Pharmacokinetic (PK) 
To assess the PK of both dose levels of miricorilant.		
Population Patients with presumed NASH.		
Number of Patients Planned Approximately 120 patients will be enrolled in the study.		

Methodology

This is a Phase2a, randomized, double-blind, placebo-controlled study conducted in 120 patients with presumed NASH, based on blood tests and noninvasive measures, to evaluate the safety, tolerability, PK, and preliminary efficacy of miricorilant. (Figure S1).

Figure S1 CORT118335-860 Study Design

Abbreviations: PK, pharmacokinetics; W, week.

Patients who are eligible for participation in the study will be randomized on Day 1 in a 1:1:1 ratio to 600 mg miricorilant, 900 mg miricorilant, or placebo, for 12 weeks of treatment. Randomization will be stratified by the presence or absence of diabetes (see Section 3.6).

Blood samples for the measurement of miricorilant plasma concentrations will be collected at Week 6 according to the PK plan.

Duration of Treatment and Duration of Study

The maximum expected duration of a patient's participation is 22 weeks consisting of the following study periods:

- Screening Period: Up to 6 weeks
- Treatment Period: Day 1 (Baseline) to Week 12
- Follow-up Period: 4 weeks after last dose of study drug

Key Inclusion Criteria

Please see Sections 4.1 and 4.2 for a complete list of all eligibility criteria.

Patients must meet the following criteria to be eligible for enrollment into this study:

- Are men or women ≥ 18 to ≤ 75 years old.
- Have a diagnosis of presumed NASH with fibrosis defined as meeting all of the following criteria:
 - a. Either:
 - (i) A historical liver biopsy within 1 year of Screening showing NASH, NAFLD Activity Score (NAS) ≥ 4 , and F1 to F3 fibrosis
 - OR
 - (ii) The following two criteria based on non-invasive measurements:

- Aspartate aminotransferase (AST) >17 U/L for women and AST >20 U/L for men AND
- FibroScan liver stiffness measurement ≥ 8.5 kPa and Controlled Attenuation Parameter (CAP) ≥ 300 dB/m in the 3 months prior to Screening or at Screening
- b. MRI-PDFF with $\geq 10\%$ steatosis
- c. Presence of 2 or more components of metabolic syndrome: type 2 diabetes treatment or fasting blood glucose ≥ 126 mg/dL, BMI ≥ 30 kg/m², hypertension treatment or blood pressure $\geq 130/85$, history of dyslipidemia, or waist circumference ≥ 102 cm (40 in) in men and ≥ 88 cm (35 in) in women
- Must have consistent alanine aminotransferase (ALT) and AST Baseline measurements, established by 2 samples obtained at least 4 weeks and no more than 6 months apart. At least one of the values must be derived from Screening safety labs; historical results within 6 months of Screening may be used to provide the second value for eligibility. Unless both samples are $\leq 1.5 \times$ the upper limit of normal (ULN), to be eligible for study entry, the difference between the first and second measurement of ALT and AST should be $\leq 50\%$. A third sample may be repeated if the variability between the first 2 values exceeds the 50% limit. If the third sample exceeds the 50% limit (compared with the first result), the patient is not eligible.
- Patients who are taking lipid-modifying therapies must be on stable doses for at least 3 months prior to Screening and unlikely to change the dose during the study (for patients taking statin medications, please see additional restrictions in exclusion criterion #15).

Key Exclusion Criteria

Patients who meet any of the following criteria will not be eligible to participate in the study:

- Women who are pregnant, planning to become pregnant, or are lactating.
- Have a BMI < 18 kg/m².
- Are currently using any medications prohibited due to the potential for drug-drug interactions (MI) with study treatments Prohibited medications (see Section 5.4.3) must be discontinued at least 5 half-lives prior to a patient receiving their first study treatment. Administration of concomitant medications (see Section 5.4) are at the discretion of the Investigator and/or the Corcept Medical Monitor.
- Have had successful weight-loss surgery prior to Screening or are planning weight-loss surgery during the study*.
*Patients who have had Roux-en-Y gastric bypass surgery or other surgical procedures that have a fundamentally altered gastrointestinal tract may not participate regardless of success of the procedure.
- Have any elective surgery planned during the study.
- Have significant alcohol consumption, defined as more than 2 drink units per day (equivalent to 20 g of ethanol) in women and 3 drink units per day (equivalent to 30 g of ethanol) in men for ≥ 3 consecutive months within 1 year prior to Screening, inability to reliably quantify alcohol intake, or score a value ≥ 8 on the Alcohol Use Disorders Identification Test (AUDIT) questionnaire.
- Use of drugs associated with NAFLD (e.g., amiodarone, methotrexate, oral or intravenous glucocorticoids, at supraphysiological doses (prednisone equivalent ≥ 5 mg/day), tamoxifen, estrogens at doses greater than those used for hormone replacement or contraception, anabolic steroids, or valproic acid) for more than 4 weeks in the 2 months prior to randomization.
- Have been treated with obeticholic acid, ursodeoxycholic acid (Ursodiol[®] and Urso[®]), pioglitazone or high-dose vitamin E (> 400 IU/day) within the 3 months prior to Screening imaging studies.
- Have had liver transplantation or plan to have liver transplantation during the study.

- Have type 1 diabetes.
- Have type 2 diabetes and:
 - An HbA1c $\geq 9.5\%$.
 - Have had an insulin dose adjustment $>10\%$ within 60 days prior to enrollment.
 - Have a requirement for glucagon-like peptide analogue (unless on a stable dose ≥ 3 months prior to Screening), a requirement for sodium/glucose cotransporter 2 (SGLT2) inhibitors (unless on a stable dose ≥ 3 months prior to Screening), or 3 or more oral anti-diabetic (OAD) agents (unless the OAD is stable and HbA1c $<8\%$).
 - Have a history of severe hypoglycemia (symptomatic hypoglycemia requiring outside assistance to regain neurologic status).
- Are currently taking a statin other than stable doses of the following: lovastatin (up to 20 mg), pravastatin, pitavastatin, simvastatin (up to 10 mg), atorvastatin (up to 20 mg), or fluvastatin (up to 20 mg). A stable dose is defined as no changes in the dose in the last 3 months prior to Screening.
- Are currently on the oral antidiabetic drug nateglinide (Starlix).

Patients currently taking the medication may participate in the study if it is appropriate to discontinue the medication, and if the patient is amenable to discontinuing the medication for a wash out period of 5 half-lives prior to the baseline assessment.
- Are currently using a medication such as digoxin with an increased risk for toxicity in the event of electrolyte changes.
- Have weight loss of greater than 10% within the last 6 months prior to Screening.
- Have abnormal screening laboratories:
 - a. AST $>5\times$ upper limit of normal (ULN)
 - b. ALT $>5\times$ ULN
 - c. Estimated glomerular filtration rate (eGFR) ≤ 60 mL/min/1.73 m²
 - d. Creatine kinase $>3\times$ ULN
- Have known or suspected cirrhosis based on the opinion of the Investigator. The list below represents possible signs of suspected cirrhosis:
 - a. Physical exam findings:
 - i. Jaundice
 - b. Laboratory findings
 - i. Direct bilirubin >0.3 (except for patients who have Gilbert's syndrome)
 - ii. Platelet count $<140,000/\mu\text{L}$
 - c. Imaging:
 - i. Evidence of portal hypertension (dilated portal vein, presence of varices)
 - ii. Evidence of a nodular liver with splenomegaly
 - d. Endoscopy:
 - i. Evidence of esophageal varices
- Have hepatic decompensation defined as the presence of any of the following:
 - Serum albumin <3.5 g/dL
 - International normalized ratio (INR) >1.3 (unless due to therapeutic anticoagulants)
 - Total bilirubin >1.3 mg/dL (except for patients who have Gilbert's syndrome)
 - History of esophageal or gastric variceal bleedings, ascites, or hepatic encephalopathy
- Have any other chronic liver disease:

- Hepatitis B as defined by presence of hepatitis B surface antigen
- Hepatitis C as defined by presence of hepatitis C virus (HCV) antibody and positive HCV RNA. Documented cured HCV infection is acceptable if >3 years from Screening visit
- History of current active autoimmune hepatitis
- History or evidence of primary biliary cholangitis
- History or evidence of primary sclerosing cholangitis
- History or evidence of Gilbert's syndrome if direct bilirubin is elevated (in addition to total bilirubin ≥ 2) or evidence of hemolysis contributing to elevated total bilirubin
- History or evidence of Wilson's disease
- History or evidence of alpha-1-antitrypsin deficiency
- History or evidence of hemochromatosis
- History or evidence of drug-induced liver disease, as defined on the basis of typical exposure and history
- Known bile duct obstruction
- Suspected or proven liver cancer
- Any other type of liver disease other than NASH

Study Drug, Dose, and Mode of Administration

Study Drug: Miricorilant tablet, 150 mg, or placebo for miricorilant tablet, 150 mg.

Dose: 600 mg or 900 mg miricorilant, or placebo.

Patients will be instructed to take a total of 6 tablets at approximately the same time each day.

- Those in the 600 miricorilant group will take 4 miricorilant tablets and 2 placebo tablets.
- Those in the 900 miricorilant group will take 6 miricorilant tablets.
- Those in the placebo group will take 6 placebo tablets.

Mode of Administration: oral administration with 8 oz (240 mL) of water, along with food.

Criteria for Evaluation

Study endpoints corresponding to study objectives are listed below.

Primary Efficacy Endpoint

Relative change from Baseline to Week 12 in liver fat content assessed by magnetic resonance imaging–proton density fat fraction (MRI-PDFF) for both dose levels of miricorilant versus placebo.

Secondary Efficacy Endpoints

The following endpoints will be assessed relative to Baseline:

- Change in liver fat content assessed by MRI-PDFF for both dose levels of miricorilant combined versus placebo.
- Proportion of patients achieving a relative reduction in liver fat content of $\geq 30\%$ by MRI-PDFF for miricorilant versus placebo.
- Absolute change in liver fat content by MRI-PDFF for miricorilant versus placebo.
- Change in AST, ALT, and gamma-glutamyl transferase (GGT) for miricorilant versus placebo.
- Change in propeptide of type III collagen (pro-C3) for miricorilant versus placebo.
- Change in enhanced liver fibrosis (ELF) score and its components (hyaluronic acid, tissue inhibitor of metalloproteinases-1 [TIMP-1], type III procollagen [PIIINP]) for miricorilant versus placebo.

Exploratory Endpoints

The following endpoints will be assessed relative to Baseline:

- Proportion of patients achieving a relative reduction in liver fat content of $\geq 50\%$ by MRI-PDFF for miricorilant versus placebo.

- Proportion of patients with complete resolution of fatty liver by MRI-PDFF for miricorilant versus placebo.

In all patients:

- Change in ACTH, serum cortisol, and serum aldosterone (pharmacodynamic assessments).
- Change in absolute body weight.
- Change in Homeostatic Model Assessment of Insulin Resistance (HOMA-IR).

In patients with diabetes:

- Change in HbA1c.
- Change in fasting blood glucose.

In patients with high blood pressure:

- Change in blood pressure.

Safety Endpoints

The following endpoints will be assessed for miricorilant versus placebo:

- Incidence of TEAEs, AEs, and SAEs.
- Changes from Baseline in clinical laboratory tests (hematology and chemistry panels).
- Changes from Baseline in physical examinations and vital sign measurements.
- Changes from Baseline in ECG parameters.

Pharmacokinetic Endpoints

- Key PK parameters estimated from steady-state plasma concentration.

Statistical Methods

Statistical Analyses

Analysis of the Primary Efficacy Endpoints

Each dose of miricorilant will be compared with placebo on the key efficacy endpoint: the relative change from Baseline in LFC assessed by MRI-PDFF, where relative change is defined as $100 \times (\text{LFC at Week 12} - \text{LFC at Baseline}) / \text{LFC at Baseline}$. The primary analysis will use a nonparametric, rank analysis of covariance (ANCOVA) that incorporates Baseline LFC as a covariate; treatment group (2 dose levels of miricorilant and placebo) and diabetes status (stratification factor) as factors; and rank relative change in LFC as the response variable. P-values for the comparisons of each miricorilant dose group to placebo will be derived from linear contrasts. The Hodges-Lehmann method will be used to estimate the median differences between groups and their 95% confidence intervals (CIs). P-values from the comparisons will not be adjusted for multiplicity.

A sensitivity analysis of the primary endpoints will be performed that requires fewer assumptions than the primary analysis. The sensitivity analysis will employ 2 Wilcoxon rank-sum tests to compare each of the miricorilant dose groups to placebo; that is, one test will compare 600 mg miricorilant to placebo and another will compare 900 mg miricorilant to placebo.

The relative change in LFC in each treatment group will be summarized by the median and 25th and 75th percentiles. The primary analysis will be performed on the Efficacy Evaluable (EE) population, which includes all patients who receive at least 1 dose of study drug and remain in the trial for at least 6 weeks.

Analysis of the Secondary Efficacy Endpoints

The secondary efficacy endpoints will be analyzed using the EE Population unless otherwise specified.

A rank ANCOVA similar to the primary analysis will be used to test for evidence of a dose-response among the 2 miricorilant dose levels. Like the primary analysis, the model will include Baseline LFC as a covariate, diabetes status as a factor, and rank relative change in LFC as the response variable. But

in contrast to the primary analysis, the dose-response model will not include the placebo group; that is, the treatment factor will include only the 2 dose levels of miricorilant. The two miricorilant dose groups will be compared to each other using linear contrasts. The Hodges-Lehmann method will be used to estimate the median difference between the dose levels and its 95% CI. A significant difference between groups will be taken as evidence of a dose-response relationship. Dose-response will also be assessed graphically using boxplots of the relative change in MRI-PDFF for each treatment group.

A set of 3 Cochran-Mantel-Haenszel (CMH) tests—one for each pairwise comparison of treatment groups – will be used to evaluate the secondary endpoint of the proportion of patients achieving a relative reduction in LFC of $\geq 30\%$ by Week 12. Each CMH test will be stratified by diabetes status. A p-value will be reported for each test along with an estimate of the common relative risk of achieving a $\geq 30\%$ reduction in LFC. Each relative risk estimate will be accompanied by a 95% CI. The percentage of patients in each group who achieve a $\geq 30\%$ reduction in LFC will be presented along with a 95% CI.

The absolute change in LFC from Baseline to Week 12 will be assessed using a parametric ANCOVA model with Baseline LFC as a covariate, diabetes status and treatment group as factors, and the arithmetic difference between LFC at Week 12 and Baseline as the response variable. Linear contrasts from the model will compare each of the 2 dose levels of miricorilant to placebo. A similar ANCOVA that excludes the placebo group will be used to assess dose-response in absolute LFC change. A linear contrast from the model will compare the 2 doses of miricorilant to each other. The least squares means and associated confidence intervals derived from each model will be reported.

Other continuous secondary endpoints that are measured more than once during treatment will be analyzed using linear mixed models for repeated measures (MMRM). These endpoints include the change in AST, ALT, GGT, pro-C3, and ELF score and each of its components (TIMP-1, PIIN, and hyaluronic acid). Restricted maximum likelihood (REML) estimation will be used. Each MMRM model will include Baseline LFC as a covariate; treatment, diabetes status, visit, and treatment by visit interaction as fixed effects; and patient within treatment group as a random effect. Comparisons of each miricorilant group to placebo and to each other will be based on the estimates from the model.

Analyses of Exploratory Endpoints

The proportion of subjects achieving a relative reduction in LFC of $\geq 50\%$, and the proportion with a complete resolution, will be analyzed using CMH tests analogous to those used to evaluate the secondary endpoint of the proportion of patients achieving a relative reduction of $\geq 30\%$.

Analyses of continuous endpoints, such as the change in ACTH, serum cortisol, and serum aldosterone from Baseline to Week 12, will be analyzed using parametric ANCOVA models with Baseline LFC as a covariate, diabetes status and treatment group as factors, and the arithmetic difference between the endpoint at Week 12 and Baseline as the response variable. Changes in HbA1c and fasting blood glucose within patients with diabetes will employ pairwise Wilcoxon rank-sum tests to compare treatment groups. A similar strategy will be used to compare groups on the change from Baseline in blood pressure among patients with high blood pressure.

Exploratory analyses will be described in the SAP finalized before database lock.

Safety Analyses

Adverse events will be mapped to system organ classes and preferred terms using the Medical Dictionary for Regulatory Activities (MedDRA). Treatment-emergent AEs will be summarized overall and displayed by system organ class and preferred term, as well as by severity, seriousness, and relationship to the study treatment. Serious AEs and AEs that lead to study treatment discontinuation or withdrawal from the study will be listed by individual patient.

Clinical laboratory test results (chemistry, hematology, and coagulation), vital sign measurements, physical examination findings, and ECG results will be summarized by visit using descriptive statistics. Shift tables will be constructed that describe changes from Baseline in clinical laboratory values.

Pharmacokinetic Analysis

The PK data obtained, including the PK parameters of miricorilant estimated by noncompartmental methods, will be summarized descriptively. The 95% CIs for the PK parameters will be presented. Additionally, plasma concentrations of miricorilant will be plotted over time.

Details of the PK analyses will be described in a PK analysis plan finalized before database lock.

Sample Size

The planned sample size is approximately 40 patients/group or approximately 120 subjects randomized 1:1:1 across 2 miricorilant treatment groups and one placebo group. The sample size calculation assumes that the SD for change in LFC due to treatment will be comparable to that observed in Patel et al. 2016, where an SD of 33% was reported, and in [Harrison et al. 2019](#), where the SD was not reported but can be estimated from confidence intervals to be about 28%. A slightly more conservative estimate of 35% is assumed for the calculation here. Assuming that placebo patients experience a reduction in LFC of 10%, 34 patients per group affords 80% power to detect a significant difference at the $\alpha=0.05$ level between either miricorilant dose group and placebo as long as the miricorilant group achieves a 35% or greater reduction in LFC. Assuming that up to 10% of patients may drop out prior to the Week 12 MRI-PDF assessment, the required sample size increases to 38 patients per group or 114 total patients. The sample size has been rounded up to 40 patients per group, or 120 total patients, for convenience. The sample size estimate has not been adjusted for multiple comparisons.

Contents

CLINICAL STUDY PROTOCOL CORT118335-860	1
Sponsor Signature Page	2
Protocol Synopsis.....	3
Contents	11

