9.5.8 Safety Analyses

Adverse events will be mapped to system organ classes and preferred terms using the Medical Dictionary for Regulatory Activities (MedDRA). TEAEs will be summarized overall and displayed by system organ class and preferred term, as well as by severity, seriousness, and relationship to the study treatment. Serious AEs and AEs that lead to study treatment discontinuation or withdrawal from the study will be listed by individual patient.

Clinical laboratory test results, vital sign measurements, and ECG interval results will be summarized as changes from Baseline by parameter by treatment and visit using descriptive statistics. Categorical laboratory results may also be summarized using shift tables.

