3.4 Safety Objective

- To assess the safety and tolerability of miricorilant versus placebo.

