9 STATISTICAL METHODS

9.1 General Statistical Consideration

Statistical analyses will be reported with tables, figures, and listings, presented in rich text format, and using recommended ICH numbering. Output specifications for all tables, figures, and listings will be in conformance with guidelines specified by the [ICH of the Electronic Common Technical Document Specification](#) (Apr 2003).

All summaries will be presented by assigned treatment group, or actual treatment group where applicable. In addition, data will be tabulated for all patients combined. All relevant data collected on the electronic case report form (eCRF) will be presented in by-patient data listings, to include the site identifier, patient number, and assigned treatment group.

In general, continuous variables will be summarized by the number of patients with non-missing data, mean, SD, median, 25th percentile, 75th percentile, minimum, and maximum values. Categorical variables will be summarized by the number and percentage of patients in each category.

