9.8 Efficacy Analyses

Due to observations related to safety, the study was terminated by the sponsor prior to completion. The sample size at the time of study termination does not support formal comparisons of the treatment groups, and therefore, no efficacy analyses specified in the protocol will be performed. Descriptive statistics for efficacy endpoints will be provided as described below.

Furthermore, no patient reached their Week 12 visit, and therefore, descriptive statistics at Week 12 will not be presented. Instead, descriptive statistics will be provided for all analysis visits up to the last non-missing visit.

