9.9 Safety Analyses

All safety analyses will be performed in the Safety Population. All safety data will appear in by-patient data listings. Unless specified otherwise, the categorical safety analyses will include both scheduled and unscheduled visits. No comparisons between treatment groups for safety measures will be made.

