9.9.1 Adverse Events

TEAEs are defined as those AEs with onset on or after the first dose date of study drug or existing events that worsened after the first dose during the study and up to and including 28 days after the last dose of study drug, per protocol. Any AEs reported more than 28 days after the last dose of study drug will be considered post-treatment AEs.

Events reported with a partial onset date (e.g., month and year are reported but the day is missing) will be considered to be treatment-emergent, as appropriate, if it cannot be confirmed that the event onset was prior to the first dose of study drug based on the available date entries.

Summaries that are displayed by system organ class (SOC) and preferred terms (PT) will be ordered by alphabetical order of SOC and by descending total incidence PT nested within each system organ class. Summaries displayed by PT only will be ordered by descending total incidence of PT.

Tabular summaries with numbers and percentages of patients that have the following adverse events will be provided:

- Overview of TEAEs
- Summary of TEAEs
- Summary of TEAEs related to study drug (defined as possibly related, probably related, or related)
- Summary of TEAEs leading to discontinuation
- Summary of Serious TEAEs
- Summary of Serious TEAEs related to study drug
- Summary of Serious TEAEs leading to discontinuation
- Summary of TEAEs with fatal outcome
- Summary of TEAEs with Grade 3 or higher

All above summaries will be presented by PT, and by PT nested within SOC. Also, summaries by maximum severity will be provided for TEAEs and Serious TEAEs.

All AEs, whether treatment-emergent or not, will be listed by treatment arm and individual patient, including dates of onset and resolution and associated study day, duration, serious, NCI-CTCAE grade (CTCAE v.5.0), action taken, outcome, and relationship to study drug. Serious TEAEs and TEAEs leading to discontinuation will also be listed separately.

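### SAP 9.9 bars between-group safety comparisons although safety is framed as miricorilant versus placebo, so no drug-minus-placebo difference with its uncertainty is reported in a trial stopped for safety

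*Protocol*

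**What the plan says.** **Objective and endpoints.** SAP 3.4 gives the safety objective as "To assess the safety and tolerability of miricorilant versus placebo", matching Protocol 2.4. The safety endpoints in the Protocol Synopsis, Protocol 3.2.4 and SAP 4.4 all open with "The following endpoints will be assessed for miricorilant versus placebo".

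**The rule in the analysis section.** SAP 9.9 states "No comparisons between treatment groups for safety measures will be made". It gives no reason and does not separate tests from estimates.

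**The context.** SAP 9.8 records: "Due to observations related to safety, the study was terminated by the sponsor prior to completion". It continues: "The sample size at the time of study termination does not support formal comparisons of the treatment groups". The consequence it draws is that the protocol's efficacy analyses will not be done. SAP 10 repeats that reasoning, again for efficacy.

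**What is planned for safety.** SAP 9.9.1: "Tabular summaries with numbers and percentages of patients that have the following adverse events will be provided". SAP 9.1: "All summaries will be presented by assigned treatment group, or actual treatment group where applicable", and SAP 7.4 makes this actual treatment for safety. SAP 9.9.3 adds counts above ALT, AST and bilirubin thresholds, shift tables, an eDISH plot and a listing of patients with liver-test abnormalities. SAP 9.7 summarises exposure duration by arm.

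**What the protocol planned.** Protocol 9.5.8 is descriptive: "TEAEs will be summarized overall and displayed by system organ class and preferred term". It names no safety test, difference or interval.

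**The concern.** The SAP asks a comparative safety question and then rules out a comparative answer. Because the study stopped on safety observations and no patient reached Week 12 (SAP 9.8), safety is the main question these data can still address: how much more often events, liver events in particular, occurred on drug than on placebo, and how uncertain that excess is.

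Percentages side by side let a reader subtract but give no measure of uncertainty. In small arms that cuts both ways: a chance imbalance can pass for a signal, and a real excess can be dismissed as noise. As worded, SAP 9.9 excludes even a descriptive difference with an interval, although only formal testing is clearly unsuited to small numbers.

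**Working it through.** **Step 1. Set the texts side by side.**

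| Place | Content |
|---|---|
| Protocol 2.4, SAP 3.4 | Safety objective is relative to placebo |
| Protocol 3.2.4, SAP 4.4 | Safety endpoints are relative to placebo |
| Protocol 9.5.8 | Descriptive methods only |
| SAP 9.8, SAP 10 | Small sample given as the reason for no formal comparisons; conclusion limited to efficacy |
| SAP 9.9 | No between-group safety comparisons; no reason |
| SAP 9.1, 9.9.1, 9.9.3 | Counts and percentages by arm; no difference, ratio or interval |

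The tension is within the SAP: 3.4 and 4.4 against 9.9.

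**Step 2. Is there a planned figure to reproduce?** No safety power or precision is stated. The only sample size (34 per group, 38 after dropout, rounded to 40) is for liver fat and does not bear on this point.

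**Step 3. Can an estimate be made at small sizes?** Neither the number treated at termination nor any event count is given, so these inputs are assumptions: zero events on placebo, 20% or 40% on drug, both doses pooled, and 2:1 drug to placebo (from the 1:1:1 allocation).

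Wilson limits for a proportion p with n patients, z = 1.96:
(p + z²/2n ± z·√[p(1−p)/n + z²/4n²]) / (1 + z²/n).

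Newcombe limits for D = p1 − p2, with l and u the Wilson limits of each arm:
lower = D − √[(p1 − l1)² + (u2 − p2)²]; upper = D + √[(u1 − p1)² + (p2 − l2)²].

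*8/20 versus 0/10.* Wilson limits are 0.2188 to 0.6134 on drug and 0 to 0.2775 on placebo. Lower = 0.40 − √(0.1812² + 0.2775²) = 0.40 − 0.331 = 0.069. Upper = 0.40 + 0.2134 = 0.613.

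*4/10 versus 0/5.* Wilson limits are 0.1682 to 0.6873 and 0 to 0.4345. Lower = 0.40 − √(0.2318² + 0.4345²) = 0.40 − 0.492 = −0.092. Upper = 0.687.

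The same formula gives the other rows, in percentage points:

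| Assumed drug vs placebo | 20% vs 0% | 40% vs 0% |
|---|---|---|
| 10 vs 5 | +20 (−26 to +51) | +40 (−9 to +69) |
| 20 vs 10 | +20 (−10 to +42) | +40 (+7 to +61) |
| 30 vs 15 | +20 (−3 to +37) | +40 (+14 to +58) |

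**Step 4. Read the table.** Identical percentages carry different evidence depending on arm size. For 40% versus 0%, the lower limit moves from −9 to +14 points as the assumed sizes rise from 10 vs 5 to 30 vs 15. An estimate with an interval can be computed at every size shown.

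**Step 5. Size of the addition.** Six outcomes times three contrasts (pooled, 600 mg, 900 mg, each against placebo) is 18 intervals.

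**The case against.** The strongest defence is that this is a matter of wording. The protocol pairs its comparative endpoint language with purely descriptive methods, so a display by arm may be all it ever meant by assessing drug against placebo, and SAP 9.9 may mean only that there will be no formal comparisons. The by-arm output is extensive, and in a very small trial the patient-level liver listing may tell a reader more than a risk difference. Intervals added after a safety termination, for outcomes close to the suspected signal, could themselves be over-read.

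Much of this stands, and it limits the point. Three stronger readings are tempting and not supported:

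- A reader might infer that the SAP removed a planned safety analysis and failed to disclose it in SAP 10. Protocol 9.5.8 specified no safety contrast, so none was removed and there was none for SAP 10 to list.
- A reader might infer that safety by arm will not be reported. SAP 9.1, 9.9.1 and 9.9.3 provide it.
- A reader might infer that efficacy is treated better because SAP 9.8.2.1 pools the doses for liver fat. That summary is also descriptive, gives no difference or interval, and follows from an endpoint specified in the protocol; no pooled safety endpoint was ever specified.

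What the defence does not remove is the unqualified sentence in SAP 9.9. It does not say formal or inferential, and it stands without a reason in the same document that twice frames safety against placebo. The risk of over-reading is an argument for labelling the intervals clearly; percentages without intervals carry that risk too.

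**Conclusion.** The point holds in a limited form and is worth acting on. SAP 9.9 conflicts with SAP 3.4 and 4.4, the restriction is unexplained, and no drug-minus-placebo difference with its uncertainty is specified for any safety measure. No planned analysis was lost and the by-arm counts remain.

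Its numerical size cannot be fixed from the documents. The intervals above rest on assumed arm sizes and event rates with no placebo events. They show that estimates are feasible and often wide; they say nothing about what this trial observed, and whether an interval excludes zero should not be used as a test.

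**What to change.** Replace the SAP 9.9 sentence with: *No hypothesis tests will be performed on safety measures.* Then add the risk difference from placebo, for both doses pooled and for each dose, with a Newcombe 95% confidence interval, for this short list:

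- any TEAE;
- any serious TEAE;
- any TEAE leading to discontinuation;
- ALT or AST above 3×ULN;
- ALT or AST above 5×ULN;
- total bilirubin above 2×ULN.

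Name the single interval method, because methods can differ at small sizes. Label the results descriptive and unadjusted for multiplicity, and present them beside exposure duration by arm (SAP 9.7), since crude proportions ignore unequal follow-up. State in SAP 10 that they were added after termination.

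The cost is SAP wording and one or two tables. Most counts are already planned; SAP 9.9.3 counts ALT and AST separately at these thresholds, so the either-enzyme categories need a simple derivation from the same data. The downside is up to 18 wide, overlapping intervals sharing one small placebo arm.
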